7.2.10 Secondary Safety Endpoints – Vital Signs

*Vital Signs evaluation included body weight (in kg with one decimal), and sitting assessments of systolic and diastolic blood pressure and pulse rate as well as respiratory rate and oral body temperature. Blood pressure and pulse rate as well as respiratory rate will be recorded after the subject has rested in the **sitting position** for at least 3 minutes. Blood pressure should be assessed on the same arm for each time of determination using an automated measurement device.*

Body temperature were assessed orally (normal below 37.5°C).

Clinically significant changes (or a clinically significant worsening) in vital signs, which were observed the first time during study will be reported as adverse event.

Vital Signs (with the exception of body weight) were assessed at Screening Visit, D-1 0hr, D-1 0.5hr, D-1 2hr, D-1 4hr, D-1 8hr, D1 0.5hr, D1 2hr, D1 4hr, D1 8hr, D1 14hr, D2 Pre-Dose, D2 0.5hr, D2 4hr, D2 8hr, D2 10hr, D2 10.5hr, D2 12hr, D4 4hr, D4 8hr, D6 4hr, D6 8hr, D6 10hr, D6 10.5hr, D6 12hr and is documented on eCRF Pages “Vital Signs”. Body weight is collected on the same eCRF at Screening Visit only.

For the secondary evaluations the documented parameters systolic and diastolic blood pressure (mmHg), pulse rate (bpm), respiratory rate (breaths/min), as well as oral body temperature (°C) will be described as well as corresponding Changes from Baseline (D-1 0hr).

7.2.11 Secondary Safety Endpoints – Laboratory Safety Data

The following laboratory evaluations will be performed at the study site:

Haematology: hemoglobin, hematocrit, RBC count, reticulocyte count, WBC with differential platelet count.

Biochemistry: sodium, potassium, chloride, calcium, inorganic phosphorus, total protein, albumin, total bilirubin, AST, ALT, alkaline phosphatase, GGT, FSH (only for postmenopausal females at Screening to confirm post-menopausal status), creatinine, BUN(urea-N), glucose, uric acid, cholesterol and high sensitivity C-reactive protein.

Urinalysis Stix: pH, density, glucose, protein, blood (free Hb), bilirubin, urobilinogen, ketones, nitrites, leukocytes and erythrocytes. A midstream urine sample (approx. 30 mL) will be obtained, in order to avoid contamination and allow a proper assessment.

The subject need not be in fasting condition.

Laboratory results will be categorized either as normal, abnormal not clinically significant, abnormal clinical significant by the investigator. Each laboratory value determined in the study as well as the clinical assessments will be entered on the eCRF.

Clinically significant changes (or a clinically significant worsening) in laboratory safety assessments, which were observed the first time during study will be reported as adverse events.

The investigator may choose to repeat any abnormal result ONCE, in order to rule out laboratory error. Repeated evaluations are mandatory until their normalization or until the time course and reason of the underlying process can clearly be assessed.

Laboratory Safety Assessments are performed at Screening Visit, Baseline Visit, FU1, FU2, FU3 and are documented on eCRF Pages “Haematology”, “Chemistry” and “Urinalysis”, respectively. These assessment may be done at any time on the scheduled examination day.

For the presentation of data, the clinical evaluation as documented on the eCRF page will be utilized, i.e. no derivation of Normal/Abnormal values will be done for analysis purposes. As a consequence, a missing clinical evaluation will be presented as missing.

For this single center study, the laboratory parameters will be presented in the units, in which they were collected, i.e. no transformation into SI units will be performed.

For the secondary evaluations, all observed hematology and biochemistry parameters (except FSH-test) will be described as well as corresponding Changes from Baseline (D-1).

The documented results for FSH and urinalysis will be listed.

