For any subject discontinuing the study, the Investigator ask the subject to undergo, as far as possible, a final medical visit to examine the subject's health conditions

- a. *This examination will verify that all values tested at screening have remained within a clinically acceptable range (i.e., not clinically significant changes compared to screening). The assessments will be conducted as detailed in Follow Up Day 16±2 (FU 3).*
- b. *Arrange for alternative medical care of the withdrawn subject, if necessary*
- c. *Report in the eCRF date and time of the last dose administration, and date and primary reason of study discontinuation*
- d. *Record in the eCRF any follow-up, if the subject is withdrawn for an AE.*

Procedures conducted at the Early Termination Visit are at the discretion of the Investigator and may be among the study procedures or additional procedures not performed during the study but deemed necessary by the investigator.

All assessments except event type data will be analyzed according to the nominal visit identifier on the eCRF page, irrespective of meeting the time window as specified in the study plan and of having the procedures performed over 1 or 2 consecutive days.

This rule does not hold for subjects, who terminate study prematurely. For these subjects, the records collected at the Early Termination Visit will be shifted to the next applicable visit assessment according to Table 2. If this is not possible, the last record will be treated as Unscheduled Assessments based on the rules below.

Unscheduled Assessments will not be considered for by-visit analyses but all collected data will be listed. Additional assessments at a given visit will be labelled under the respective Visit label. However, the respective timepoint will be labelled as “xx hr U1”, “xx hr U2”, etc. with xx indicating the number of the last scheduled assessment time before the unscheduled assessment plus a consecutive sequence number.

Unscheduled Assessments which were not taken on a scheduled visit will be labelled as “Unscheduled Visit x.01 U1”, “Unscheduled Visit x.02 U1”, “Unscheduled Visit y.01 U1” etc. indicating the number of the last preceding visit plus a consecutive sequence number. If more than one unscheduled assessment is done at the same day, the assessments will be labeled consecutively “Unscheduled Visit x.01 U1”, “Unscheduled Visit x.01 U2”.

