The **Treatment Period** starts with the first intake of study medication and ends before the first assessment of the D7 visit. Any assessment before the first intake of study medication is allocated to the **Screening Period**. The **Follow-Up Period** of the study will start with the first assessment on the D7 visit.

Moreover, the Treatment Period is divided into **Treatment Period of the Single Dose Scheme**, which ends before the first intake of study medication on D2 and the **Treatment Period of the Multiple Dose Scheme**, which starts with the first intake of study medication on D2.

If not stated otherwise in subsequent sections, Baseline is defined as the first assessment of the D-1 Visit.

Change from Baseline is defined as the difference between an assessment and the respective first assessment at the Baseline Visit.

Change from Multiple Dose Baseline is defined as the difference between an assessment and the respective Pre-Dose assessment at the D2 Visit.

A **Time-Matched Change from Baseline** is defined as the difference between an assessment and the respective assessment at the corresponding time-point at the Baseline Visit.

Table 2: Study Visits

Scheduled Visit	Scheduled Visit Label	Scheduled Relative Assessment Times within Visit	Comments
Screening Visit	Screening	Before Baseline Visit	Acceptable time window for screening visit: Treatment Day -21 to Treatment Day -2
Baseline Visit	D-1	0 hr 0.5 hr 2 hr 4 hr 8 hr 9 hr 10 hr 11 hr 12 hr 14 hr 16 hr	Acceptable time window: Day before first dose
Treatment Day 1	D1	Pre-Dose 0 hr 0.5 hr 2 hr 4 hr 8 hr 9 hr 10 hr 11 hr 12 hr 14 hr 16 hr	Dosing should occur at 0 hr Time of dosing should be identical to respective time point at baseline visit.
Treatment Day 2	D2	Pre-Dose 0 hr 0.5 hr 2 hr 4 hr 6 hr 8 hr 10 hr 10.5 hr 11 hr 12 hr 13 hr 14 hr 16 hr	Dosing should occur at 0, 2, 4, 6, 8, 10 hr. Time of dosing should be identical to respective time points at baseline visit.

Scheduled Visit	Scheduled Visit Label	Scheduled Relative Assessment Times within Visit	Comments
Treatment Day 3	D3	Pre-Dose 0 hr 2 hr 4 hr 6 hr 8 hr 10 hr	Dosing should occur at 0, 2, 4, 6, 8, 10 hr. Time of dosing should be identical to respective time points at baseline visit.
Treatment Day 4	D4	Pre-Dose 0 hr 2 hr 4 hr 6 hr 8 hr 10 hr	Dosing should occur at 0, 2, 4, 6, 8, 10 hr. Time of dosing should be identical to respective time points at baseline visit.

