10.7.3 Laboratory Safety Data

For the secondary analyses, the raw values as well as the changes from baseline haematology and chemistry (except of FSH) will be summarized by treatment for the SAF.

All collected and derived laboratory safety data will be listed for the SAF.

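### A laboratory reading that its repeat shows to be an error stays in the haematology and biochemistry tables, because the SAP has no rule putting the valid repeat in its place

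*SAP*

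**What the plan says.** **Repeats.** On laboratory data, SAP 7.2.11 (repeating Protocol 8.7) states: "The investigator may choose to repeat any abnormal result ONCE, in order to rule out laboratory error". It also requires further repeats until a value normalises or its cause is understood, and has every laboratory value entered on the eCRF. It does not say which reading is the analysis value.

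**Visit rules.** SAP 7.1 sets the general rule: "All assessments except event type data will be analyzed according to the nominal visit identifier on the eCRF page". On extra readings it says: "Unscheduled Assessments will not be considered for by-visit analyses but all collected data will be listed". It continues: "Additional assessments at a given visit will be labelled under the respective Visit label", with a U1, U2 suffix on the time point. On baseline: "If not stated otherwise in subsequent sections, Baseline is defined as the first assessment of the D-1 Visit". SAP 7.2.11 takes changes from D-1 without naming a different reading.

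**Tables.** SAP 10.7.3 plans that "the raw values as well as the changes from baseline haematology and chemistry (except of FSH) will be summarized by treatment for the SAF". In SAP section 12 these are Tables 14.4-3.1, 14.4-3.2, 14.4-4.1 and 14.4-4.2. The readings themselves go to Listings 16.2.08-4.1 and 16.2.08-4.2.

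**Grades.** The investigator grades each result as normal, abnormal but not clinically significant, or abnormal and clinically significant. SAP 7.2.11 says: "For the presentation of data, the clinical evaluation as documented on the eCRF page will be utilized", and adds that no normal/abnormal flag will be derived.

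**The concern.** The purpose of the repeat is to find out whether the original reading was wrong. A plan that then tabulates the original regardless of the answer defeats that purpose in the tables. Changes in haematology and biochemistry are named secondary safety endpoints, and safety and tolerability are the primary objective. With 20 and 10 subjects and no inferential analysis, the descriptive tables are the main by-arm laboratory evidence, and one wrong value can create or mask a visible difference between arms.

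D-1 is the most exposed visit. Laboratory findings count towards eligibility there (inclusion criterion 7e), so an abnormal result is likely to be repeated, and a baseline error is carried into every later change.

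A smaller, separate matter is that numeric summaries do not show how many subjects in each arm moved from normal to abnormal.

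**Working it through.** **1. Which reading is tabulated?**
- An extra reading at a scheduled visit keeps the visit label and gets a U1 or U2 time point. In describing that label, SAP 7.1 itself calls the extra reading unscheduled.
- A repeat taken on another day is labelled as an unscheduled visit.
- Unscheduled readings are left out of by-visit analyses. A confirmatory repeat is therefore listed only, whichever day it is taken.
- At D-1 the first reading is baseline, so the original is used there too.

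**2. Does another rule override this?**
- SAP 8.3.2 takes the data as recorded, with no imputation.
- SAP 5.1 refers data quality control to the Data Management Plan but states no rule on repeats.
- SAP 8.3.3 has the blind data review meeting (BDRM) decide which subjects and visits are evaluable. Its listed scope is re-screened subjects, treatment and study-eye assignment, protocol deviations with analysis sets, and sight-threatening events. Laboratory errors are not among them.

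No contrary rule is stated.

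**3. How far can one value move a table?** Arm sizes are 20 (rhNGF) and 10 (vehicle), from SAP 3.2. The documents give no laboratory error size or SD. I assume an error of k SD of the tabulated quantity, with k = 3, 5 and 10.

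- Shift in the arm mean = k/n.
- Added variance: the affected value lies k(1 − 1/n) from the shifted mean, and each of the other n − 1 values moves k/n from it. The sum of squares is k²(n − 1)/n; dividing by n − 1 gives k²/n. The expected SD is therefore multiplied by about √(1 + k²/n).

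| k | Mean shift, n = 20 | SD factor, n = 20 | Mean shift, n = 10 | SD factor, n = 10 |
|---|---|---|---|---|
| 3 | 3/20 = 0.15 SD | √1.45 = 1.20 | 3/10 = 0.30 SD | √1.90 = 1.38 |
| 5 | 5/20 = 0.25 SD | √2.25 = 1.50 | 5/10 = 0.50 SD | √3.50 = 1.87 |
| 10 | 10/20 = 0.50 SD | √6.00 = 2.45 | 10/10 = 1.00 SD | √11.0 = 3.32 |

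The difference between arms moves by the same amount as the affected arm's mean.

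**4. How many summaries does it reach?** Laboratory tests after dosing are at FU1, FU2 and FU3. An error at one of these affects one raw-value summary and one change summary. An error at D-1 affects one raw-value summary and three change summaries, 1 + 3 = 4, each change being wrong by the same amount with opposite sign.

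**5. Where do the grades appear?** The four laboratory tables are titled as values or changes from baseline. None names a grade or a shift. A first clinically significant change is reported as an adverse event (SAP 7.2.11) and, if treatment-emergent, counted by arm in the TEAE tables (SAP 10.6.1). What no by-arm table names is the result that is newly abnormal but not clinically significant.

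**The case against.** **On repeats.** The SAP never names laboratory repeats when it speaks of unscheduled assessments, so the conclusion is an inference. A confirmed error might be corrected on the eCRF under the Data Management Plan, or dealt with by a query at the BDRM. That is possible, but neither document says so, and the rules that are written lead the other way. Keeping scheduled values also has a good reason: only abnormal results are repeated, so routine replacement would pull the data towards normal. This stands, and it is why replacement should be limited to confirmed errors.

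**On the tables.** A reader might infer more than the documents support.
- *That the tables use only the first scheduled reading.* There is a stated exception for subjects who stop early: "the records collected at the Early Termination Visit will be shifted to the next applicable visit assessment according to Table 2".
- *That newly abnormal results go uncounted by arm.* This is too broad, because new clinically significant changes enter the TEAE tables.
- *That the recorded grade is never used.* The sentence in SAP 7.2.11 mainly says where any displayed flag comes from. It promises no table, the grade may appear in the listings, and the mock shells are in a separate document.
- *That a large true rise in one subject would be lost in a mean.* SAP 8.1 also plans the minimum, median and maximum. The largest rise would appear as the maximum, and one false value would hardly move the median. The maximum cannot, however, tell a true value from an erroneous one.

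**On the shift table.** The haematology and biochemistry endpoint is change from baseline, and the SAP delivers it. A shift was specified only for urinalysis, and SAP 3.6 discloses why it was dropped: no interpretation was recorded. No promised haematology or biochemistry analysis is missing.

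**Conclusion.** The point on repeats holds. Under the written rules, a reading that its repeat shows to be a laboratory error remains in the mean, SD, extremes and changes from baseline, and the valid reading is only listed. The movement is 0.15 to 0.50 SD in the rhNGF mean or 0.30 to 1.00 SD in the vehicle mean, if one error occurs and is 3 to 10 SD in size. Those sizes are assumptions, and the documents give no basis for how often such an error would arise; it may never happen.

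Severity is low. No test, error rate or decision rule depends on these tables, and both readings can be found in the listings. The shift table is an improvement to the presentation, not the correction of an error.

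**What to change.** **Rule for repeats.** Add to SAP 7.2.11: where the original result is judged to be a laboratory error, and this is documented before unmasking at the BDRM, the confirmatory repeat is the analysis value for that visit, D-1 included, and both readings are listed. In all other cases, including repeats taken to follow a value to normalisation, the original scheduled value stands. Add this review to the BDRM scope in SAP 8.3.3, and a cross-reference in SAP 7.1 so that the general rules on unscheduled readings and baseline do not override it.

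**Optional table.** Add one by-arm shift table for haematology and biochemistry, by parameter, from the D-1 investigator grade to the worst post-dose grade, using the three categories already on the eCRF. Say whether unscheduled readings count towards the worst grade, and apply the rule above where an error was confirmed.

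**Cost.** A few sentences, one flag set at the BDRM and one extra table. No new data are needed.

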7.2.12 Secondary Safety Endpoints – Intraocular Pressure

Intraocular Pressure testing will be performed per eye using Goldmann Tonometer and the resulting values (mmHg) are recorded on the eCRF page “Intraocular Pressure” at Screening Visit, Baseline 0hr, FU2 8 hr, FU3 0 hr.

Clinically significant changes (or a clinically significant worsening) in IOP, which were observed the first time during study will be reported as adverse event.

The change from baseline will be derived per eye for all scheduled post-baseline visits as differences from Baseline (D-1 0hr).

7.2.13 Secondary Safety Endpoints – Best Corrected Distance Visual Acuity (BCDVA)

Vision must be measured for each eye separately using ETDRS visual acuity chart at 4 meters (13 feet) and, if indicated, also at 1 meter (i.e. when less than 20 letters were read at 4m).

Clinically significant changes (or a clinically significant worsening) in BCDVA, which were observed the first time during study will be reported as adverse event.

In case both tables on the eCRF page have been completed (at 4 meter and at 1 meter) then the visual acuity score is the sum of the total number of correct letters from both tables. If only the table at 4 meter is completed and the overall number of letters read is 20 or above then the Visual Acuity Score is the number of total letters read at 4 meter plus 30.

If no letter were read at 4 and 1 meter, the best visual potential ability of the subject is selected from: a) count fingers; b) hand motion; c) light perception; or d) no light perception. The Visual Acuity Score is then set to 0.

The Snellen Equivalent is defined as the acuity equivalent for the smallest line with 1 or no error. The logarithm of the minimal angle of resolution (logMAR) is calculated as “- log (Snellen Equivalent)” with two decimals precisions. The logMAR ranges from 0.30 (20/10) to 1.60 (20/800) and an increase in logMAR reflects a worsening of visual acuity. If for a subject only ability for counting fingers is reported, logMAR will be set to 2.00; if for a subject only recognition of hand motion is reported, logMAR will be set to 3.00 (Holladay 1997).

Visual acuity is assessed for each eye at Screening Visit, Baseline Visit 0hr, D1 8hr, D2 Pre-Dose, D2 8hr, D3 Pre-Dose, D6 Pre-Dose, D6 8hr, FU1 0hr, FU2 8hr, FU3 0hr and are documented on the eCRF page “Best Corrected Distance Visual Acuity”.

The change from baseline will be derived for Visual Acuity Score and LogMAR per eye for all scheduled post-baseline visits as differences from Baseline (D-1 0hr).

7.2.14 Secondary Safety Endpoints – Tear Film Break Up Time

TFBUT will be measured per eye by determining the time to tear break-up. The TFBUT will be performed after instillation of 5 µl of 2% preservative-free sodium fluorescein solution into the inferior conjunctival cul-de-sac of each eye. The subject will be instructed to blink several times to thoroughly mix the fluorescein with the tear film. In order to achieve maximum fluorescence, the examiner should wait approximately 30 seconds after instillation before evaluating TFBUT. With the aid of a slit lamp at 10X magnification using cobalt blue illumination, the examiner will monitor the integrity of the tear film, noting the time it takes to form lacunae (clear spaces in the tear film) from the time that the eye is opened after the last blink. This measurement will be performed within 10 seconds maximum. The TFBUT will be measured twice during the first minute after the instillation of the fluorescein. If the 2 readings differ by more than 2 seconds a third reading is taken. The TFBUT value will be the average of the 2 or 3 measurements.

Clinically significant changes (or a clinically significant worsening) in TFBUT, which were observed the first time during study will be reported as adverse event.

TFBUT is assessed for each eye at Screening Visit, Baseline Visit 0hr, D1 8hr, D2 Pre-Dose, D2 8hr, D3 Pre-Dose, D6 Pre-Dose, D6 8hr, FU1 0hr, F U2 8hr, FU3 0hr and is documented on the eCRF page “Tear Film Break Up Time”.

For the secondary analysis, the mean TFBUT (sec) value will be derived from the 2 or 3 documented single values per eye and will be presented with same number of digits as done for the raw values (i.e. 2 digits). The calculated average as provided in the eCRF will not be used for the analysis.

The change from baseline will be derived for mean TFBUT (sec) per eye for all scheduled post-baseline visits as differences from Baseline (D-1 0hr).

7.2.15 Secondary Safety Endpoints – Ocular Surface Staining

As grading scale of the corneal and conjunctiva damage, the NEI/Industry Workshop guidelines will be used [2]. The cornea is divided into five sectors (central, superior, inferior, nasal and temporal), each of which is scored on a scale of 0–3, with a maximal score of 15.

For the investigation of the conjunctiva, the nasally and temporally conjunctiva is divided into a superior paralimbal area, an inferior paralimbal area and a peripheral area with a grading scale of 0–3 and with a maximal score of 9 for the nasal and temporal conjunctiva, respectively.

Briefly, on the grading scale used grade 0 reflects normal/healthy situation, whereas grade 3 reflects a severe damage in each considered sector.

Corneal Staining will be derived as sum of scores of the five corneal sectors (central, superior, inferior nasal and temporal) ranging from 0 to 15. Corneal Staining score will only be calculated, if all 5 sector scores are available.

Conjunctival Staining will be derived as sum of scores of the conjunctival area (nasal-superior paralimbal, nasal-inferior paralimbal, nasal-peripheral, temporal-superior paralimbal, temporal-inferior paralimbal, temporal-peripheral) ranging from 0 to 18. Conjunctival Staining will only be calculated, if all 6 area scores are available.

Both scores will be derived for each eye separately. No imputation will be envisaged for these parameters.

Ocular Surface Staining is assessed for each eye at Screening Visit, Baseline Visit 0hr, D1 8hr, D2 Pre-Dose, D2 8hr, D3 Pre-Dose, D6 Pre-Dose, D6 8hr, FU1 0hr, FU2 8hr, FU3 0hr and are documented on the eCRF page “Corneal Fluorescein Staining”.

The change from baseline in corneal staining as well as conjunctival staining will be derived per eye for all scheduled post-baseline visits as differences from Baseline (D-1 0hr).

